6.1.4.2 Visit Window for Visits in Withdrawal Period

Visits within withdrawal period will be mapped per visit window defined in [Table 6.1](#) below for efficacy and safety data collected in withdrawal period except of binge eating diary data. For diary data, see [Section 5.1.1](#) for data derivation rule.

Table 6.1: Visit Window for Clinic Visits in Withdrawal Period for Non-Binge Eating Diary Data

Variables to be Applied	Time Interval (Day) ^a	Target Time Point (Day)	Analysis Visit (label on output)
CSSA, DESS	-5 to 1 ^(b)	0	Withdrawal Baseline
	2 – 10 ^(c)	7	Withdrawal Week 1
	11 – 17 ^(c)	14	Withdrawal Week 2
	18 – EOS ^(c)	21	Withdrawal Week 3
Other	-5 to 3	0	Withdrawal Baseline
	4 – 10	7	Withdrawal Week 1
	11 – 17	14	Withdrawal Week 2
	18 – EOS	21	Withdrawal Week 3
^a Relative to the day of the last dose of double-blind study medication ^b per phone contacts or clinic visits ^c for clinic visits only.			

If a subject has 2 or more visits in one analysis visit window, the visit closest to the targeted day will be used as the study visit for that analysis visit window. The other additional visit(s) will be denoted as an unscheduled visit and not included in the by-visit descriptive summary analyses. However, measurements from this/these other additional visit(s) may be included in the other safety analyses to assure all off-treatment measurements are included. If the 2 study visits occur with the same number of days from the target day within the same visit window, the later one will be considered as the study visit for that target day.

Non-clinic phone contact visits within withdrawal period will be mapped per visit window defined in [Table 6.2](#) below for CSSA and DESS specifically.

Table 6.2: Visit Window for Non-Clinic/Phone Contact Visits in Withdrawal Period

Variables to be Applied	Time Interval (Day) ^a	Target Time Point (Day)	Analysis Visit (label on output)
CSSA, DESS	1 – 2	1	Day 1-2
	3 – 4	3	Day 3-4
	5 – 6	5	Day 5-6
	7 – 8	7	Day 7-8
	9 – 10	9	Day 9-10
	11 – 12	11	Day 11-12
	13 – 14	13	Day 13-14
	15 – 16	15	Day 15-16
	17 – 18	17	Day 17-18
	19 – 20	19	Day 19-20
	21 – 22	21	Day 21-22
	23 – 24	23	Day 23-24
	25 – EOS ^(b)	25	≥ Day 25

^a Relative to the day of the last dose of open-label study medication
^b per phone contacts visits only.

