5.2.2. Withdrawal Assessment for Physical Dependence and Withdrawal Symptoms

Subjects who either are early terminated in treatment period or complete 12-week treatment period but not enter into extension study need to complete the study medication withdrawal period assessments and visits.

Assessment of potential withdrawal effects will be conducted via administration of the CSSA, DESS, HAM-A, and MADRS at Week 12 (End of Treatment), then again at Weeks 13, 14, and 15 during the 3-week study medication withdrawal period. The CSSA and DESS will also be completed during the 3-week study medication withdrawal period on non-clinic visit days. Clinical site staff will call the subject every other day during the study medication withdrawal period, beginning the second day after the last dose of study drug, unless a clinic visit is scheduled for that day. Clinical site staff will record the responses in the subject’s source information and in the CRF with the contact date and time. A window of ± 1 day is allowed for each weekly clinic visit and telephone call. If the subject cannot be contacted on a given day, during the next contact the study site staff will retrospectively collect the missed CSSA and DESS, in addition to the current day’s CSSA and DESS.

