6.1.1.2. Withdrawal Period (Off Treatment)

For subjects who either are early terminated from DB period or complete DB period but do not enter the extension, withdrawal period analyses will be generated; no withdrawal period analyses will be produced for subjects entering the extension study.

The withdrawal period will begin with immediately after the last study dose. Study day relative to the last study dose date will be denoted as Day 0. The end of the withdrawal period is defined as the maximum of last study visit (scheduled or unscheduled) and last phone contact after the

321

last study dose. If the last study dose date is missing (eg, lost follow-up subjects), start and end days will be set as missing.

Each subject’s assessment at each visit (site or phone contact) in the withdrawal period will be assigned a study day with respect to start date of the withdrawal period.

- Study Day = Assessment date – start date of the withdrawal period if assessment date \geq start date of the withdrawal period

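### SAP Table 6.2 sets each phone-contact target one day before the planned call, so an allowed one-day-late call can push the next on-time CSSA/DESS rating out of the by-visit summary

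*SAP*

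**What the plan says.** **Schedule.** SAP Section 5.2.2 states: "Clinical site staff will call the subject every other day during the study medication withdrawal period, beginning the second day after the last dose". No call is made on a day that has a clinic visit. On leeway it adds: "A window of ± 1 day is allowed for each weekly clinic visit and telephone call". If a contact fails, the missed CSSA and DESS are collected retrospectively at the next contact. Protocol Sections 7.1 and 11.8.10 agree.

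**Day count.** SAP Section 6.1.1.2 states: "Study day relative to the last study dose date will be denoted as Day 0". Table 3 likewise starts the withdrawal period at Day 0, the day of the last double-blind dose.

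**Rows and targets.** SAP Section 6.1.4.2, Table 6.2, maps phone contacts to rows 1-2 (target 1), 3-4 (target 3), 5-6 (target 5), up to 23-24 (target 23) and 25 onward (target 25). Its footnote a reads: "Relative to the day of the last dose of open-label study medication". Table 6.1, in the same section, counts from the last double-blind dose.

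**Selection.** The same section says: "If a subject has 2 or more visits in one analysis visit window, the visit closest to the targeted day will be used". A tie goes to the later visit. An unselected visit is relabelled as unscheduled and left out of the by-visit descriptive summaries, though it may enter other safety analyses.

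**Use.** SAP Section 7.4.6 summarises CSSA and DESS by treatment and visit, covering both clinic and non-clinic contacts.

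**The concern.** A closest-to-target rule works only if the target is the day on which the contact is planned. In Table 6.2 every even-day planned call sits on the last day of its row and one day past its target. A call made one day late, as the plan allows, therefore lands exactly on the next row's target and beats the call planned for that row. The rule then prefers the off-schedule rating to the on-schedule one.

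Withdrawal effects after abrupt stopping are a stated objective (Protocol Section 5.3), and the phone contacts give the only view finer than weekly. The CSSA looks back 24 hours (SAP Section 5.2.2.1), so the day of the rating matters. At stake is whether the every-other-day profile shows the ratings it was designed to show.

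**Working it through.** **Planned days.** Day 0 is the last dose, so the second day after it is Day 2. Clinic visits fall on Days 7, 14 and 21 (Protocol Section 11.8.10 and the Table 6.1 targets), and a call is skipped on a clinic day. Every other day from Day 2 gives Days 2, 4, 6, 8, 10, 12, 16, 18 and 20, which is 9 calls.

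**Check of the day count.** The Table 6.1 targets of 7, 14 and 21 match the planned clinic days on this count. The Table 6.2 targets of 1, 3, 5 and so on do not match the planned calls. They would match only if Day 0 were the day after the last dose, which Table 3 rules out.

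**One call late by a day, the others on time.**

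| Planned | Made on | Row (target) | On-time call in that row | Kept | Left out |
|---|---|---|---|---|---|
| 2 | 3 | 3-4 (3) | 4 | 3 | 4 |
| 4 | 5 | 5-6 (5) | 6 | 5 | 6 |
| 6 | 7 | 7-8 (7) | 8 | 7 | 8 |
| 8 | 9 | 9-10 (9) | 10 | 9 | 10 |
| 10 | 11 | 11-12 (11) | 12 | 11 | 12 |
| 12 | 13 | 13-14 (13) | none (Day 14 is clinic) | 13 | none |
| 16 | 17 | 17-18 (17) | 18 | 17 | 18 |
| 18 | 19 | 19-20 (19) | 20 | 19 | 20 |
| 20 | 21 | 21-22 (21) | none | 21 | none |

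In each displacement the distances are 0 for the late call and 1 for the on-time call. The next on-time rating is displaced in 7 of 9 cases. It is 6 of 9 if the Day 6 case is set aside, because a late Day 6 call falls on the Day 7 clinic visit. The late call's own row has no rating from that day's contact in 9 of 9. One day early gives 0 displaced and 0 empty, so the fault concerns late calls only.

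**Size, if calls are independently late by one day with probability 0.10 (an assumption).**
- On-time ratings dropped: 7 of the 9 calls have a call planned two days before them, so 7/9 × 0.10 = 7.8%.
- Planned rows empty, before any retrospective rating: a late call's row is refilled only if the preceding call is also late. For 7 calls the chance is 0.10 × 0.90 = 0.09; for Days 2 and 16 it is 0.10. (7 × 0.09 + 2 × 0.10)/9 = 9.2%.
- At 20% late the dropped share is 7/9 × 0.20 = 15.6%.

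**If the count restarts after each clinic visit.** The calls are then 2, 4, 6, 9, 11, 13, 16, 18 and 20. Only late calls on Days 2, 4, 16 and 18 displace the next one: 4/9 × 0.10 = 4.4%. The Week 2 calls (9, 11, 13) already sit on their targets.

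**Possible repairs, on the even-day schedule.**
- Same rows, targets moved to 2, 4, 6 and so on: displacement falls from 7 of 9 to 0 of 9, and early calls lose nothing. A late call's own row is still empty in 9 of 9, because the row closes on the planned day.
- Rows 2-3, 4-5 and so on: late calls cause no empty rows, but early calls now do. At 10% early only, empty rows go from 0% to (7 × 0.09 + 2 × 0.10)/9 = 9.2%. At 10% each way they are 9.2% under both layouts.
- No set of non-overlapping two-day rows can hold a full one-day leeway either side of calls planned two days apart.

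**The case against.** **The selection rule is printed before Table 6.2 is introduced.** Its application there is an inference. It is the natural one, since the rule stands in the shared section and a target column has no other use, but the SAP should say so.

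**Retrospective collection may fill the empty row.** This stands in part. If the call was late because contact failed, a rating dated to the missed day fills that row. The SAP does not state the dating, and the Day 3 rating would still displace the Day 4 one.

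**Displacement needs the next call to be on time.** This also stands. If every call runs one day late, nothing is displaced; each rating simply moves to the next row.

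**The consequence is small.** The protocol's withdrawal endpoints are CSSA and DESS change at Weeks 13, 14 and 15, for which Table 6.1 uses clinic visits only. The phone rows are descriptive, all data are listed, and no efficacy result is touched.

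**Stronger readings a reader might infer.** One could add displaced and empty rows and call about 17% of planned rows wrong at 10% late. That overstates it: rows are labelled by days since the last dose, so a Day 3 rating does belong in Day 3-4, and the total rests on an assumed late-only pattern. One could infer from the footnote that the table was copied from another study; the documents show only a wrong word. One could say that some rows have no planned call, but for row 13-14 that depends on the schedule reading, and the last rows can serve as catch-alls. A Day 1 call could serve as both Withdrawal Baseline and first result, but only when no closer rating exists, such as one on Day 0, and its frequency is unknown.

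**Conclusion.** The targets in Table 6.2 are one day early relative to the SAP's own call schedule and day count. Applied as stated, the closest-to-target rule lets an allowed late call remove the next on-time CSSA or DESS rating from the by-visit summary, for 7 of 9 planned calls on the even-day schedule. At an assumed 10% late rate about 8% of on-time ratings are dropped, or about 4% if the count restarts after clinic visits. The documents give no late rate, so these percentages scale with whatever rate occurs.

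The conclusion rests on Day 0 being the last dose, which the SAP states, and on the selection rule covering Table 6.2, which it implies. The effect is confined to the descriptive phone-contact rows. It does not support any claim that the Week 13-15 withdrawal endpoints, or any efficacy analysis, are compromised.

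**What to change.** **Preferred.** Assign each phone rating to its planned call number, allowing one day either side, and summarise by call number. A lone contact on an odd day could be one call late or the next call early. The SAP therefore needs to take the call number from the CRF, if it is recorded there, or state a tie rule before unblinding.

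**Minimum.** Keep the rows and move the targets to the planned call days (2, 4, 6 and so on). On the even-day schedule this ends displacement of on-time ratings but leaves a late call's own row empty. State which schedule is meant. If the count restarts after each clinic visit, the Week 2 targets should stay on Days 9, 11 and 13; moved to 10, 12 and 14, a Day 11 call made on Day 10 would beat an on-time Day 9 call.

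**In either case.** State that the closest-to-target rule applies to Table 6.2 if day rows are kept, date retrospective ratings to the missed day, and change open-label to double-blind in footnote a. Do not adopt rows 2-3, 4-5 and so on, which only move the empty rows from late calls to early ones.

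**Cost.** An edit to one table, its footnote and a few sentences before database lock. Contact dates are already recorded on the CRF, so the minimum fix needs no new data.

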6.1.5 Protocol Amendment for Region Stratification

6.1.5.1 Stratification Error of ‘Region’

The original protocol (version 1.0) and amendment 1 (version 2.0) stated that the randomization was to be balanced using permuted blocks with 2 stratification criteria: (1) baseline number of binge eating days per week and (2) regions in the United States, which were defined in the Interactive Response Technology System (IRT) User Requirements Specification and is provided in [Attachment 9.2.2](#). For sake of convenience, hereafter in this document, terms of IXRS and IRT are used interchangeably.

In total 50 sites participated in this study. The study team noticed on July 20, 2017 that stratification by region was not implemented as planned, that is to say, the initiated sites in IXRS were linked to incorrect regions. As of July 20, 2017, a total of 44 sites were screening subjects and 137 subjects from 35 sites had already been randomized. A full investigation was immediately requested by Sponsor to IRT vendor (Oracle). According to the incident report (Incident Number: INC000004665171) provided by Oracle, the root cause of this mistake was with a third party software tool used to develop the IXRS system; more specifically, the mistake was caused by the software’s component related to a dropdown list for “region” selection . Region field should have been populated with the set of initial sites that Sponsor provided to Oracle and then should have been populated by Sponsor for all other sites. Once a site was added, the “region” selection should have been disabled. Due to the unexpected behavior of the software component, the “region” value was sometimes overwritten. Based on this investigation

321

report, in one scenario, a consistent pattern for region selection was identified: when a new site was added in “Manage Sites”, the “region” dropdown was loaded as a blank value, and eventually the “region” value assignment would be moved up by one row in the database. In other scenarios, a consistent pattern for region selection was not identified. IXRS vendor noted that there was no way for them to reproduce how the data was assigned in this trial.

6.1.5.2 IXRS Update

Although unexpected region assignment of sites may not be truly random in a statistical sense, region allocation appears inconsistent and no clear pattern was found. To minimize the impact of the region strata error on data interpretation, the study team decided to amend the IXRS and study protocol to remove the regional stratification factor due to the following considerations.

- (1) Once a site was initiated in the IXRS system, its associated region was determined and could not be changed. When the mistake was found, 44 of the 50 planned sites had been incorrectly linked to incorrect regions; by the time that IXRS eventually could have been fixed, 47 out the 50 sites would have been linked to incorrect regions. This means that about 85%~90% randomized subjects were to have been linked to incorrect region. Therefore, the regional stratification of subjects would no longer have been meaningful.
- (2) Incorrectly linked regions of the study sites show no overall consistent patterns according to the investigation report issued by the IXRS vendor. Two-dimensional distribution of sites by initial planned region in IRT User Requirements Specifications (URS) vs. the region actually assigned by IXRS (see [Attachment 9.2.3](#)) seems to support that regions were assigned nearly randomly before IXRS amendment.
- (3) Initial purpose of stratification by region was solely to balance the treatment allocation within a region for this United States study. Differences in treatment response among US regions were not expected, nor was the sponsor’s intention to detect potential US regional differences. The stratification strategy was chosen for optimization purposes and should not be treated as necessary.

IXRS URS was amended and signed off on Aug 09, 2017 (V7.0). The updated IXRS went alive on Aug 23, 2017. By removing the stratification factor ‘Region’, study SEP360-321 essentially adopted the same stratification criterion as study SEP360-221. Data analysis methods in protocol amendment 2 (V3.0) of this study are similar to what was planned and performed for study SEP 360-221.

6.1.6 Pooling Strategy for Analysis of Centers

Study SEP360-321 is a multicenter study conducted in the United States. In principle, all centers with 18 or fewer subjects are pooled based on geographic proximity if necessary, with the intention that no pooled center contains more than 36 randomized subjects. The list of pooled centers for the study based on the pooling strategy described above is provided in [Attachment 9.2.1](#) and finalized prior to database lock of the study.

Similarly, planned region and actual region (defined in Section 6.1.7) will be pooled based on geographic proximity as well if a region has 18 or fewer subjects. The list of pooled regions is provided [Table 6.3](#) in [Section 6.1.7](#).

6.1.7 Definition of Planned Region Group and Actual Region Group ('Modified' Region Strata)

To assess the robustness of primary and key efficacy analyses, two region-related exploratory efficacy analyses for primary and key secondary endpoints will be conducted. For each randomized subject, two region variables are defined as below:

- **Planned region group:** unless otherwise specified, it is defined per URS of original IRT (see [Attachment 9.2.2](#)).
- **Actual region group** (or equivalently, 'Modified' region strata): defined as

Case 1: for subjects randomized PRIOR to the IXRS update:

Actual region is equal to the region strata value.

Case 2: for subjects randomized AFTER the IXRS update and from an 'old' site, where an old site is defined as the one with at least one subject randomized prior to the IXRS update (see [Attachment 9.2.3](#)):

Actual region is same as the corresponding region strata value of the site per IXRS data.

Case 3: for subjects randomized AFTER the IXRS update and from a 'new' site, where a new site is defined as the one without any subject randomized prior to the IXRS update but having at least one subject randomized after the IXRS update (see [Attachment 9.2.3](#)):

Actual region will be assigned with the corresponding planned region value per URS of original IXRS if location of the new site (ie, State) was listed in the URS of original IXRS (see [Attachment 9.2.2](#)); otherwise, the planned region and actual region will be assigned as 'Undefined' since the new site is not listed in URS of original IXRS.

Numbers of subjects within each planned and actual region are listed in [Table 6.3](#) as below. As of the completion of study enrollment, there is one site (site 067), which has 3 randomized subjects, from a location that was not listed in original URS of IXRS. In addition, the actual

321

region ‘Central 2’ is small and has only 3 subjects. To make sure exploratory analyses related to the planned region and actual region are feasible, small planned and actual regions will be pooled for analysis purposes. Specifically, for planned region, site ‘067’ will be pooled with the initial planned region ‘Central 1’ to generate a pooled planned region still named as ‘Central 1’; no pooling is needed for other planned regions; for actual region, site ‘067’ and initial actual region ‘Central 2’ will be pooled with the initial actual region ‘Central 1’ to generate a pooled actual region named as ‘Central1/Central 2’; no pooling is needed for other actual regions. Numbers of subjects within each pooled planned and actual region are listed in [Table 6.3](#) as well and are finalized prior to database lock of the study. The exploratory efficacy analyses are to be performed as needed by replacing term of ‘pooled center’ with pooled actual region or pooled planned region group in the corresponding statistical analysis to further corroborate primary and key secondary efficacy results.

Table 6.3 Pooled Planned and Actual Region Groups Used for Exploratory Efficacy Analyses

Planned Region Group		Pooled Planned Region Group		Actual Region Group		Pooled Actual Region Group	
Region Name	Number of Subjects	Region Name	Number of Subjects	Region Name	Number of Subjects	Region Name	Number of Subjects
Northeast	59	Northeast	59	Northeast	127	Northeast	127
East	75	East	75	East	37	East	37
Central 1	50	Central 1^(a)	53	Central 1	138	Central 1 /Central 2^(b)	144
Central 2	69	Central 2	69	Central 2	3		
Southeast 1	55	Southeast 1	55	Southeast 1	62	Southeast 1	62
Southeast 2	22	Southeast 2	22	Southeast 2	17	Southeast 2	17
West 1	88	West 1	88	West 1	24	West 1	24
West 2	70	West 2	70	West 2	80	West 2	80
Undefined	3			Undefined	3		

Note: (a): Site 067 from Michigan (undefined in URS of IXRS) is pooled with initial region ‘Central 1’.

(b): Site 067 and actual region ‘Central 2’ are pooled with actual region ‘Central 1’.

6.1.8 Adjustments for Covariates

MMRM model and ANCOVA model contain baseline as a covariate to adjust baseline. Other covariates may be included for modeling purposes, as specified.

6.1.9 Analysis Populations

The Intent-to-Treat (ITT) Population: All randomized subjects who receive at least one dose of study medication and have at least 1 post-baseline result in any efficacy evaluation. The ITT population is the primary population for efficacy analyses, ie, unless otherwise specified, all efficacy analyses are based on ITT population.

The Per Protocol (PP) Population: All ITT subjects who have no major protocol violations that may affect the interpretation of the primary efficacy endpoint. The PP population will be used to assess robustness of the primary efficacy analysis. Major protocol violations and the PP population will be determined through a blinded data review meeting (BDRM) and identified prior to the database lock.

Subjects in the ITT and PP populations will be analyzed based on the treatment to which they are randomized.

The Double-blind (DB) Safety Population: All randomized subjects who receive at least one dose of study medication. The DB safety population mainly is used for the data analyses of the safety data collected through Week 12 or during the treatment period. Subjects are analyzed based on the actual treatment received; specifically, for subjects who are randomized to dasotraline 6 mg group and dosed with dasotraline 4 mg but never titrated to dasotraline 6 mg (ie, early terminated on or prior to Week 2 visit), the actual dose will be dasotraline 4 mg; otherwise, actual dose will be set as dasotraline 6 mg; In the event that a subject receives a treatment other than the one to which he/she is randomized or expected, the actual treatment is defined as the treatment to which the subject is exposed for the greatest duration during the treatment period. The actual treatment is generally the same as the randomized treatment group, unless the subject takes incorrect/unexpected dose during the entire study. Hereafter, DB safety population will be referred as safety population by default.

The Withdrawal Population: The withdrawal population includes all randomized subjects who receive at least one dose of study medication, and either discontinues the study drug during the treatment period before the Week 12 visit or completes the 12-week treatment period but do not enter the extension study (Study SEP360-322), and have at least 1 assessment after the last study drug for any safety or efficacy evaluation. The withdrawal population mainly is used to summarize the safety/efficacy assessments collected in the withdrawal period except of adverse event data.

The Modified Withdrawal Population: all subjects in the withdrawal population plus the subjects who do not enter the extension study and do not enter the withdrawal period, but the last study dose dates are at least 2 days earlier than the last study visit. The modified withdrawal population will be mainly used for adverse event that could be retrospectively collected.

Withdrawal analyses will be presented by planned treatment group for efficacy data and by actual treatment group for safety data.

Pharmacokinetics (PK) Population: The PK population is defined as all subjects who are randomized, receive at least 1 dose of study drug, and have any post-baseline plasma concentrations sample collection of dasotraline.

6.1.10 Stratification Factor ‘Baseline Number of Binge Days’ vs. Baseline Number of Binge Days Group

Group of Baseline number of binge days is defined as: Baseline number of binge days ≤ 4 , Baseline number of binge days >4 ; this group should be essentially equivalent to the stratification factor unless there is a subject stratified into the incorrect stratum. The stratification factor (ie, Baseline binge days category) will be consistently used in the statistical models, when applicable, for efficacy analysis as described in this document. Compared with the stratification factor, group of Baseline number of binge days will be used in the other scenarios, including the statistical models based analyses for safety variables.

